3.4.5 Other Restrictions and Precautions

- Medications with known or potential anti-HCV activity other than the assigned study treatment are prohibited during the on treatment period
- Any prescription or herbal product which is not prescribed by the investigator or licensed physician for treatment of a specific clinical condition is prohibited
- Methadone and buprenorphine should be used with caution. These drug levels may change with concomitant use of DCV and SOF
- Long-term treatment (\geq 2 weeks) with agents that are immunosuppressive, or have a high risk for nephrotoxicity or hepatotoxicity, should be discussed with the central medical monitor

3.5 Discontinuation of Subjects following any Treatment with Study Drug

Subjects MUST discontinue investigational product (and non-investigational product at the discretion of the investigator) for any of the following reasons:

- Subject's request to stop study treatment
- Any clinical adverse event (AE), laboratory abnormality or intercurrent illness which, in the opinion of the investigator, indicates that continued participation in the study is not in the best interest of the subject
- Termination of the study by Bristol-Myers Squibb (BMS)

- Loss of ability to freely provide consent through imprisonment or involuntarily incarceration for treatment of either a psychiatric or physical (eg, infectious disease) illness
- Pregnancy
- Laboratory or Clinical Criteria: If any of the following laboratory or clinical criteria is obtained for any patient, the result must be repeated /confirmed within 72 hours and the BMS central medical monitor should be informed. If the results are confirmed, the patient must discontinue treatment. Clinical criteria must have Principal Investigator or Sub-Investigator assessment prior to proceeding to permanent discontinuation
 - Evidence of confirmed hepatic decompensation (Child-Pugh Class B or C, Score > 6)
 - ALT > 2 × baseline and 5 × ULN, and either total bilirubin > 2 × ULN or INR > 2
 - Any Grade 4 AE or clinically significant laboratory abnormality considered study drug-related (see [Section 6.3](#) for laboratory abnormality AE reporting requirements).
- Virologic Breakthrough (confirmatory results must be obtained 2 weeks from the original result) defined as:
 - Confirmed $\geq 1 \log_{10}$ IU/mL HCV RNA on-treatment increase from nadir, or
 - Confirmed increase in HCV RNA \geq LLOQ if HCV RNA previously declined to < LLOQ TD/TND.

If discontinuation of therapy is required, this must occur no later than the next study visit.

Any subject who receives anti-HCV therapy in the post-treatment period prior to Post-Treatment Week 4 (ie, a subject who discontinued therapy due to an AE or virologic failure), who then chooses to receive an alternative therapy (outside of the study), should discontinue from the study after completing the Post-Treatment Week 4 safety visit (see [Table 5.1-3](#)). If the subject receives HCV therapy after Post-Treatment Week 4, the subject should be discontinued from the study as soon as possible, following completion of the procedures outlined in the Post-Treatment Week 24 visit.

The investigator must notify the BMS Medical Monitor/designee in the event that a female subject becomes pregnant within 24 hours and submit information to WWS on the pregnancy form within 24 hours. The study drug should be discontinued after pregnancy has been confirmed.

All subjects who discontinue study drug should comply with protocol specified follow-up procedures as outlined in [Section 5](#). The only exception to this requirement is when a subject withdraws consent for all study procedures including post-treatment study follow-up or loses the ability to consent freely (ie, is imprisoned or involuntarily incarcerated for the treatment of either a psychiatric or physical illness).

The end of the study is defined as the date of the last visit for the last subject to complete the study. The last visit is defined as the last post-treatment follow up subject visit.

If study treatment is discontinued prior to the subject's completion of the study, the reason for the discontinuation must be documented in the subject's medical records and entered on the appropriate case report form (CRF) page.

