3.3.1 Inclusion Criteria

1) Signed Written Informed Consent

- a) Freely given informed consent must be obtained from subjects prior to clinical trial participation, including informed consent for any screening procedures conducted to establish subject eligibility for the study.

2) Target Population

- a) Subjects must be able to understand and agree to comply with the prescribed dosing regimens and procedures, report for regularly scheduled study visits, and reliably communicate with study personnel about adverse events and concomitant medications.
- b) Subjects chronically infected with HCV genotype 3, as documented by positive HCV RNA at screening and either:
 - i) Positive anti-HCV antibody, HCV RNA, or a positive HCV genotype test at least 6 months prior to screening; **OR**
 - ii) Liver biopsy consistent with chronic HCV infection at screening (or a liver biopsy performed within 36 months prior to enrollment with evidence of chronic Hepatitis C such as the presence of fibrosis).
- c) HCV RNA \geq 10,000 IU/mL at Screening
- d) Subjects who are HCV-treatment naive with no previous exposure to any:

- i. Interferon formulation (ie IFN α , peg-IFN α) or RBV
- ii. HCV direct acting antivirals (DAAs)

OR

- e) Subjects who are HCV-treatment experienced:

- i. All anti-HCV therapies (for example, IFN α with or without RBV, SOF/RBV, cyclophilin inhibitors and inhibitors of microRNA) are permitted with the exception of previous exposure to NS5A inhibitors.
- ii. All permitted prior anti-HCV therapies must be discontinued or completed ≥ 12 weeks prior to screening.

Documentation of prior virologic response to treatment is desirable but not strictly required.

- f) Subjects with compensated cirrhosis. Determination of cirrhosis status is required prior to randomization. A biopsy is not needed for participation. Cirrhosis will be defined as any one of the following:

- i. Liver biopsy at any time prior to Screening showing cirrhosis (Metavir $> F3$, Ishak > 4 , or equivalent), OR
- ii. Most recent Fibroscan with a result of ≥ 14.6 kPa within ≤ 1 year of Baseline/Day 1, OR
- iii. FibroTest score of ≥ 0.75 AND an APRI of ≥ 2 at Screening

In the absence of a definitive diagnosis of presence or absence of cirrhosis by the above criteria, a liver biopsy is required. Liver biopsy supersedes Fibroscan which supersedes FibroTest.

- g) Body Mass Index (BMI) of 18 to 40 kg/m², inclusive at Screening.

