- For **female partner**, who is a WOCBP, of a male subject participating in the study may use Progestogen-only oral hormonal contraception where inhibition of ovulation is not the primary mode of action (**Note: Progestogen only hormonal contraception is NOT an acceptable method of contraception for WOCBP female subjects.**)

*A male and a female condom must not be used together

Azoospermic males, women who are not of childbearing potential and WOCBP who abstain from heterosexual activity on a continuous basis are exempt from contraceptive requirements. However, WOCBP who abstain from heterosexual activity on a continuous basis must still undergo pregnancy testing.

UNACCEPTABLE METHODS OF CONTRACEPTION

- 1) Periodic abstinence (calendar, symptothermal, post-ovulation methods)
- 2) Withdrawal (coitus interruptus)
- 3) Spermicide only
- 4) Lactation amenorrhea method (LAM)

3.3.2 *Exclusion Criteria*

1) Target Disease Exceptions

- a) HCV genotypes other than GT-3 infection and mixed genotype infections are not permitted.
- b) Absence of cirrhosis (subject must meet inclusion criteria of compensated cirrhosis).

2) Medical History and Concurrent Diseases

- a) Liver or any other organ transplant (including hematopoietic stem cell transplants) other than cornea and hair;
- b) Current or known history of cancer (except in situ carcinoma of the cervix or adequately treated basal or squamous cell carcinoma of the skin) within 5 years prior to screening;
- c) Documented or suspected HCC, as evidenced by previously obtained imaging studies or liver biopsy (or on a screening imaging study/liver biopsy if this was performed);
- d) Evidence of decompensated liver disease including, but not limited to, radiologic criteria, a history or presence of ascites, bleeding varices, or hepatic encephalopathy;
- e) Evidence of an ongoing medical condition contributing to chronic liver disease other than HCV (such as, but not limited to: hemochromatosis, autoimmune hepatitis, metabolic liver disease, alcoholic liver disease, toxin exposures);
- f) History of chronic hepatitis B virus (HBV) as documented by HBV serologies (eg, HBsAg-seropositive). Subjects with resolved HBV infection may participate (eg, HBsAb-seropositive with concurrent HBsAg-seronegative);
- g) Any gastrointestinal disease or surgical procedure that may impact the absorption of study drug. (Subjects who have had cholecystectomy are permitted to enter the study);

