- b) Total bilirubin ≥ 2 mg/dL (≥ 34 μ mol/L), unless due to Atazanavir/Ritonavir treatment or subject has a documented history of Gilbert's disease
- c) Albumin < 3.0 g/dL (30 g/L);
- d) Platelets $< 50 \times 10^3$ cells/ μ L;
- e) ANC $< 0.75 \times 10^3$ cells/ μ L;
- f) Hemoglobin < 10 g/dL (100 g/L);
- g) Creatinine Clearance (CrCl) ≤ 50 mL/min (as estimated by Cockcroft and Gault);
- h) Alpha fetoprotein (AFP):
 - i. AFP > 100 ng/mL (> 82.6 IU/mL) **OR**
 - ii. AFP ≥ 50 and ≤ 100 ng/mL (≥ 41.3 IU/mL and ≤ 82.6 IU/ mL) requires a liver ultrasound and subjects with findings suspicious for HCC are excluded.
- i) QTcF or QTcB > 500 mSec

4) Allergies and Adverse Drug Reaction

- a) History of hypersensitivity to drugs with a similar biochemical structure to DCV, SOF, and RBV
- b) Any other criteria or known contraindication that would exclude the subject from receiving DCV, SOF, and RBV

5) Prohibited Treatments and/or Therapies

- a) Exposure to any investigational drug or placebo within 4 weeks of study drug administration
- b) Use of amiodarone for 60 day time period prior to start of treatment

Refer to [Section 3.4.1](#) for prohibited and/or restricted treatments during treatment, re-treatment and post-treatment

6) Sex and Reproductive Status

- a) Males and females who do not or cannot meet the requirements outlined in Inclusion Criteria 3
- b) Male subjects must confirm that their female sexual partners are not pregnant at the time of screening

7) Other Exclusion Criteria

- a) Prisoners or subjects who are involuntarily incarcerated. (Note: under certain specific circumstances a person who has been imprisoned may be included or permitted to continue as a subject. Strict conditions apply and Bristol-Myers Squibb approval is required).
- b) Subjects who are compulsorily detained for treatment of either a psychiatric or physical (eg, infectious disease) illness
- c) Any other medical, psychiatric, and/or social reason which, in the opinion of the investigator would make the subject inappropriate for the study

Eligibility criteria for this study have been carefully considered to ensure the safety of the study subjects and that the results of the study can be used. It is imperative that subjects fully meet all eligibility criteria.

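### Bilirubin accepted at entry under the atazanavir/ritonavir or Gilbert's exemption can by itself meet the mandatory Child-Pugh stopping score, which has no matching exemption and no baseline reference

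*Protocol*

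**What the plan says.** **Entry.** Protocol 3.3.1 (2f) reads "Subjects with compensated cirrhosis. Determination of cirrhosis status is required prior to randomization". It then defines cirrhosis by biopsy, Fibroscan or FibroTest with APRI, but it does not define compensated. Protocol 3.3.2 (2d) excludes "Evidence of decompensated liver disease including, but not limited to, radiologic criteria, a history or presence of ascites, bleeding varices, or hepatic encephalopathy". Among the laboratory exclusions in 3.3.2, 3b removes total bilirubin of 2 mg/dL or more "unless due to Atazanavir/Ritonavir treatment or subject has a documented history of Gilbert's disease", with no ceiling for those two groups. Exclusion 3c removes albumin below 3.0 g/dL, so 3.0 g/dL and above is acceptable. The entry criteria in the supplied text do not mention a Child-Pugh score.

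**Stopping.** Protocol 3.5 opens its laboratory and clinical list with "If any of the following laboratory or clinical criteria is obtained for any patient". It asks for repeat or confirmation within 72 hours and for the medical monitor to be told, and continues: "If the results are confirmed, the patient must discontinue treatment". It adds: "Clinical criteria must have Principal Investigator or Sub-Investigator assessment prior to proceeding to permanent discontinuation". The first listed criterion is "Evidence of confirmed hepatic decompensation (Child-Pugh Class B or C, Score > 6".

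**Analysis.** Protocol 8.4.2.1 and SAP 7.5.1 compute SVR12 on all treated subjects and compare the lower 95% confidence limit with 79%. Discontinuation due to adverse events is part of a secondary endpoint (Protocol 8.3.3).

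**The concern.** The entry rule recognises that bilirubin can be high for a reason that does not bar entry. The stopping rule uses a score in which bilirubin is a component and makes no such allowance. It is also absolute: it looks at the score on the day, not at the change since Day 1. The next item in the same list does refer to baseline (ALT relative to baseline), as does the liver-injury definition in Protocol 6.6, so the protocol uses baseline elsewhere when it wants to.

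A site following both rules to the letter could enrol a subject under 3b and then have to stop that subject when the first on-treatment laboratory panel gives the same score as at entry. Repeating the test would not resolve this, because a stable value confirms itself.

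Two results are exposed. The subject stays in the all-treated denominator for SVR12 after a shortened course. The stop may also be counted among discontinuations due to adverse events: Protocol 6.3 asks for laboratory abnormalities that led to discontinuation to be captured on the adverse event forms, while Section 6 defines an adverse event as new or worsening. Without a baseline score, an entry state and a deterioration cannot be told apart.

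**Working it through.** **Inputs from the documents.** Bilirubin limit and exemption: Protocol 3.3.2, 3b. Albumin limit 3.0 g/dL: 3.3.2, 3c. Stopping score above 6: Protocol 3.5. n = 75, threshold 79%, and 68/75 with 95% CI 81.7% to 96.2%: Protocol synopsis and SAP Table 5.1-1. Exact binomial interval: SAP 7.5.

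**Assumption.** The documents do not print the Child-Pugh bands. I use the conventional ones: five items, each scored 1 to 3, minimum total 5. Bilirubin below 2 / 2-3 / above 3 mg/dL scores 1 / 2 / 3. Albumin above 3.5 / 2.8-3.5 / below 2.8 g/dL scores 1 / 2 / 3. INR below 1.7 scores 1. Ascites and encephalopathy score 1 each, because 2d excludes both. The protocol's pairing of Class B or C with a score above 6 fits this scale.

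**Step 1: score at entry.** Score = bilirubin + albumin + INR + ascites + encephalopathy, with INR below 1.7:

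| Albumin (g/dL) | Bilirubin < 2 | Bilirubin 2-3, exempt | Bilirubin > 3, exempt |
|---|---|---|---|
| > 3.5 | 1+1+1+1+1 = 5 | 2+1+1+1+1 = 6 | 3+1+1+1+1 = **7** |
| 3.0-3.5 | 1+2+1+1+1 = 6 | 2+2+1+1+1 = **7** | 3+2+1+1+1 = **8** |

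The first column holds everyone without the exemption; the maximum there is 6, so the stopping score is not met. Scores above 6 occur only in the exempt columns.

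**Step 2: dependence on the assumed bands.** The 2-3 mg/dL cell depends on where the bilirubin and albumin cut-points lie. The > 3 mg/dL column depends less on them. The exemption has no cap, so wherever the top bilirubin cut-point falls, some admissible value lies above it, scores 3 and gives a total of at least 3+1+1+1+1 = 7.

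**Step 3: the plan's own figure.** The exact lower limit for x of n is the 2.5% quantile of Beta(x, n-x+1). For 68/75 the exact interval is 81.71% to 96.16%, matching the stated 81.7% to 96.2%. For 67/75 the lower limit is 80.06%, and for 66/75 it is 78.44%. With exactly 75 treated, the conclusion against 79% therefore changes between 66 and 67 responders. (The synopsis calls 68 the minimum; that is a separate matter.)

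**Step 4: what a stopped subject could cost.** One responder turned into a failure costs 1/75 = 1.33 points. For illustration, let k subjects be stopped with SVR probability p and the rest have true SVR12 of 91%. Power = P[Bin(75-k, 0.91) + Bin(k, p) ≥ 67]. Both k and p are assumptions:

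| k | p = 0 | p = 0.5 | p = 0.8 |
|---|---|---|---|
| 0 | 76.9% | 76.9% | 76.9% |
| 1 | 65.2% | 71.6% | 75.5% |
| 2 | 51.1% | 65.9% | 74.0% |

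The documents do not say which row applies; k = 0 is possible.

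**The case against.** **Entry already requires compensated disease.** Exclusion 2d is open-ended, and a site could apply the 3.5 definition at screening and exclude anyone scoring above 6. This carries weight against a broad claim: a reader might infer that the criteria generally let decompensated subjects in, and the documents do not support that. It does not remove the conflict. If 2d is read to cover a subject whose score is above 6 only because of exempt bilirubin, it cancels the exemption that 3b grants that subject. If 2d does not cover the subject, 3.5 stops the subject on treatment.

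**Investigator assessment comes before a permanent stop.** It does, and an investigator might well not regard drug-related or Gilbert's bilirubin as hepatic decompensation. So a stop is possible rather than certain. But the step is written for clinical criteria, the score here is driven by a laboratory value, and the text gives no ground for setting aside a confirmed score.

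**Some tables are not in the supplied text.** The screening outline (Table 5.1-1), the laboratory list (Table 5.3.1-1) and the cART table (Table 3.4.2-1) could contain relevant checks. For that reason no claim is made about INR. A reader might infer a second route to a score of 7 from the lack of a visible INR limit combined with low albumin. That would need both a gap in tables that cannot be seen here and a site that disregards 2d.

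**Early stoppers remain in the analysis.** They are followed for 24 weeks after treatment (Protocol 3.1) and can still reach SVR12. This stands, and it limits the effect on the primary result.

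**Conclusion.** The conflict is real but narrow. For subjects admitted under the bilirubin exemption in 3b, the entry rule and the mandatory stopping score can apply to the same unchanged state, and the protocol does not say which prevails. This rests on the conventional Child-Pugh bands; the case above 3 mg/dL needs only the five-item, 1-to-3-point structure. Subjects without the exemption and with INR below 1.7 are not touched.

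The size cannot be derived from the documents, because the number of exempt subjects is not given and may be zero. Per subject the cost is at most 1.3 points of SVR12, and only if the subject stops and fails instead of responding, plus a possible entry in the discontinuation count.

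A reader might go further and infer that the SVR12 result would no longer describe 24 weeks of treatment in compensated cirrhosis. The documents do not support that. The primary endpoint is defined on all treated subjects whatever duration they complete, early stoppers are followed, and nothing shows that the subgroup is large enough to change what is being estimated.

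**What to change.** - Reconcile Protocol 3.3.2 (2d and 3b) with 3.5. State in 3.5 how bilirubin accepted at entry under the exemption, and the baseline score, are treated when the stopping score is applied. The sponsor's clinical team must decide which rule stands; this review proposes none.
- Record the baseline Child-Pugh score where its components are collected, so that a later score above 6 can be read as a change or as the entry state.

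The cost is protocol wording and one derived baseline variable. The downside is that a few subjects may be handled differently at screening or on treatment.

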3.1 Study Design and Duration

The study design schematic is presented in [Figure 3.1-1](#).

Figure 3.1-1: Subjects with GT-3 Infection with Cirrhosis

Study Design

Subjects with GT-3 Infection with Cirrhosis

AI444379 is an open-label trial evaluating the combination therapy of DCV + SOF with RBV for 24 weeks in subjects infected with HCV GT-3 with compensated cirrhosis. Subjects with cirrhosis who are mono-infected with HCV genotype 3 or coinfecte^d with HCV genotype 3 and HIV-1 infection will be permitted to enroll. The study will include approximately 75 subjects.

Subjects will receive the combination of DCV 60 mg QD (unless otherwise dictated by concomitant combination anti-retroviral therapy [cART] therapy) + SOF 400 mg QD + RBV (weight based 1000 mg-1200 mg daily) for 24 weeks. HCV RNA will be available for review by the clinical site personnel. After treatment is completed, subjects will be followed for 24 weeks. Subjects who discontinue early should be followed for 24 weeks post-treatment.

The primary analysis is SVR12 and the final analysis is SVR24.

Duration of study:

The screening/enrollment period is anticipated to be approximately 8 weeks from FPFV to LPFV. Study duration will be 52 weeks (4 week screening period, 24 weeks of therapy, and 24 weeks of follow-up).

Virologic Failure:

Virologic breakthrough is defined as:

1. Any confirmed ≥ 1 log₁₀ increase in HCV RNA from nadir, OR;
2. Any confirmed HCV RNA \geq LLOQ after HCV RNA $<$ LLOQ, TD or TND while on treatment

Subjects who meet a definition of viral breakthrough will discontinue therapy. If discontinuation of therapy is required, this must occur no later than the next study visit following confirmation of breakthrough.

Viral relapse is defined as:

Confirmed HCV RNA \geq LLOQ in post-treatment follow-up after HCV RNA $<$ LLOQ, TND at EOT

Long-term follow-up study: Following completion of the follow-up period of the study, select subjects at selected sites may be asked to enroll into a separate long term observational 3 year follow-up study to evaluate durability of response (if SVR is achieved) or persistence of possible drug-resistant virus (if treatment failure occurs). It is not a requirement for all subjects to enroll into the long term follow-up, and this option may not be available.

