- h) Subject Re-enrollment: This study permits the re-enrollment of a subject that has discontinued the study as a pre-treatment failure (ie, subject has not been randomized / has not been treated) up to one time. If re-enrolled, the subject must be re-consented.
- i) Subjects with HCV monoinfection or HCV/HIV-1 coinfection.
 - i. Subjects with HCV/HIV-1 coinfection must currently be receiving cART (See [section 3.4.2](#) for permitted cART), have CD4 cell count >200 cells/ μ L at screening, HIV RNA <40 copies/mL at screening and must be <200 copies/mL within 8 weeks prior to screening.

3) Age and Reproductive Status

- a) Males and Females, ≥ 18 years of age
- b) Women of childbearing potential (WOCBP) must have a negative serum or urine pregnancy test (minimum sensitivity 25 IU/L or equivalent units of HCG) within 24 hours prior to the start of study drug.

- c) Women must not be breastfeeding
- d) WOCBP must agree to follow instructions for method(s) of contraception for the following duration:
 - i. For the duration of treatment and for a total of 6 months post-treatment completion or time specified by country-specific RBV label, whichever is longer.
- e) Men who are sexually active with WOCBP must agree to follow instructions for method(s) of contraception for the following duration:
 - i. For the duration of treatment with RBV and for 6 months post-treatment completion, or per local guidelines, whichever is longer. In addition, male subjects must be willing to refrain from sperm donation during this time
- f) Azoospermic males are exempt from contraceptive requirements. WOCBP who are continuously not heterosexually active are also exempt from contraceptive requirements, and still must undergo pregnancy testing as described in this section.

Investigators shall counsel WOCBP, and male subjects who are sexually active with WOCBP, on the importance of pregnancy prevention and the implications of an unexpected pregnancy. Investigators shall advise on the use of highly effective methods of contraception, which have a failure rate of < 1% when used consistently and correctly.

At a minimum, subjects must agree to use two methods of contraception. This would include:

- 1) Any 2 Highly Effective Methods indicated below, or
- 2) 1 Highly Effective method and one Less Effective Method.

HIGHLY EFFECTIVE METHODS OF CONTRACEPTION

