The following assessment listed in [Table 5.3.1-1](#) will be analyzed by a central laboratory or other BMS specified laboratory. Subjects are not required to be fasting prior to any laboratory assessments.

All protocol-specified laboratory tests specified in [Table 5.3.1-1](#) must be analyzed and reported by the central lab. In exceptional cases when local laboratory tests are performed, central lab samples should be submitted at the same time, if possible (in addition to the time points specified in [Section 5.1](#)). In an effort to limit laboratory data collection, only relevant local lab results should be reported on the appropriate Supplementary Lab CRF pages. Refer to [Section 6.3](#) for guidance on the reporting of lab abnormalities.

Pregnancy testing must be completed for WOCBP monthly during post-treatment (Weeks 4, 8, 12, 16, 20, and 24) for WOCBP receiving RBV (see Table 5.1-3). Pregnancy testing may be performed at home if an in-office visit is otherwise not required. Telephone contacts are required to obtain results for all subjects who perform post-treatment at-home pregnancy testing. Although testing may be performed with home pregnancy testing kits, any positive result must be confirmed by serum pregnancy testing at study site.

The Roche COBAS® AmpliPrep/COBAS® TaqMan® HCV Test (LLOQ = 15 IU/mL) will be used to measure HCV RNA levels. The Versant HCV genotype 2.0 assay (LIPA) will be used for all genotype/subtype assessments. For samples where HCV genotype or subtype results are unavailable or inconclusive, the Abbott RealTime HCV Genotype II assay or viral sequence analysis may be used for genotype/subtype assessments. HCV RNA and HCV genotype will be analyzed by the central laboratory.

5.3.2 *Imaging Assessment for the Study*

Not Applicable.

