2 STUDY DESCRIPTION

2.1 Study Design

Study design schematic is presented in Figure 2.1-1.

Figure 2.1-1: Study Design Schematic

Subjects with GT-3 Infection with Cirrhosis

AI444379 is an open label, one-arm trial evaluating the combination therapy of DCV and SOF plus RBV for 24 weeks duration in GT-3 subjects with cirrhosis.

Subjects will receive the combination of DCV 60 mg QD (unless concomitant HIV regimen dictates otherwise) + SOF 400 mg QD + RBV (weight based 1000 mg-1200 mg daily) for 24 weeks.

As an open label study, HCV RNA will be available for review by the clinical site personnel. Any subject who discontinues therapy before the protocol-defined treatment duration should have 24 weeks of post-treatment follow-up. The screening/enrollment period is anticipated to be approximately 8 weeks from FPFV to LPFV. Study duration will be 52 weeks (4 week screening period, 24 weeks of therapy, and 24 weeks of follow-up).

Any subject who receives anti-HCV therapy in the post-treatment period prior to Week 4 (i.e., a subject who discontinued therapy due to an AE or virologic failure who then chooses to receive an alternative therapy outside of the study), should discontinue from the study after completing the post-treatment Week 4 safety visit. If the subject receives HCV therapy after post treatment Week 4, the subject should be discontinued from the study as soon as possible, following completion of the procedures outlined in the Post-treatment Week 24 visit.

The end of the study is defined as the date of the last visit for the last subject to complete the study. The last visit is defined as the last post-treatment follow up subject visit.

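### As far as the visible text shows, Section 3.5 ends participation at post-treatment Week 4 for subjects who start other HCV therapy before then, with no stated exception for women still due monthly pregnancy tests after ribavirin

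*Protocol*

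**What the plan says.** **Exit rule.** Protocol Section 3.5 covers subjects who receive other anti-HCV therapy before post-treatment Week 4. It describes them as people who stopped study treatment for an adverse event or virologic failure and then chose treatment outside the study. Such a subject "should discontinue from the study after completing the Post-Treatment Week 4 safety visit". SAP Section 2.1 has the same instruction: "should discontinue from the study after completing the post-treatment Week 4 safety visit". Neither visible text mentions WOCBP.

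**Testing rule.** Protocol Section 5.3.1 says: "Pregnancy testing must be completed for WOCBP monthly during post-treatment (Weeks 4, 8, 12, 16, 20, and 24"), for those receiving ribavirin. It adds: "Pregnancy testing may be performed at home if an in-office visit is otherwise not required". Telephone contact is then required to obtain the result.

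**Contraception period.** Under Section 3.3.1, WOCBP use contraception during treatment and "for a total of 6 months post-treatment completion or time specified by country-specific RBV label, whichever is longer".

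**Follow-up rules.** Another sentence of Section 3.5 sends everyone who stops study drug into the Section 5 follow-up procedures. Its only stated exceptions are withdrawal of consent for all procedures and loss of the ability to consent freely. More generally, Section 3.1 says: "Subjects who discontinue early should be followed for 24 weeks post-treatment". Sections 3.6 and 5.3.3 are to similar effect, as is SAP 2.1: "Any subject who discontinues therapy before the protocol-defined treatment duration should have 24 weeks of post-treatment follow-up".

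**Therapy started later.** The next sentence of Section 3.5 reads "If the subject receives HCV therapy after Post-Treatment Week 4, the subject should be discontinued from the study as soon as possible", once the procedures of the post-treatment Week 24 visit have been done.

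**The concern.** The protocol sets monthly pregnancy tests after treatment because of ribavirin. It does not let contraception stand in for testing: Section 3.3.1 requires tests even of WOCBP who are continuously abstinent. The exit rule removes a woman from the study when only the first of those tests is due, with most of her contraception period still to run.

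A site holding such a patient has two instructions that pull apart. Section 3.5 tells it to end her participation. Section 5.3.1 tells it that her tests must be done through Week 24. The sentence in 3.5 that limits exceptions to consent also leaves no room for an exit because of other HCV therapy. The visible text does not say which instruction governs.

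What is at stake is scheduled detection of a pregnancy in the ribavirin risk period. The efficacy result is not involved.

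**Working it through.** **Inputs**
- Post-treatment tests at Weeks 4, 8, 12, 16, 20 and 24 (Section 5.3.1).
- Exit after the Week 4 visit (Section 3.5, SAP 2.1).
- Contraception for at least 6 months after treatment (Section 3.3.1). Six calendar months are 181 to 184 days.
- Telephone contacts at Weeks 8, 16 and 20 (Section 5.8.3).
- About 75 subjects (Section 3.1).

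**Step 1: reproduce the schedule.** Every 4 weeks from Week 4 to Week 24 gives 4, 8, 12, 16, 20, 24. That is 6 tests, as in Section 5.3.1. In days after treatment: 28, 56, 84, 112, 140, 168.

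**Step 2: tests left after a Week 4 exit.** Kept: Week 4. Lost: Weeks 8, 12, 16, 20 and 24. That is 5 of 6, or 5/6 = 83%. Three of the five lost tests fall in telephone-contact weeks (8, 16, 20) and two in visit weeks (12, 24).

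**Step 3: time without scheduled testing because of the rule.** 168 − 28 = 140 days = 20 weeks. As a share of the 6-month contraception period:
- 140/181 = 77.3%
- 140/184 = 76.1%
- in weeks, 20/26 = 76.9%

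**Step 4: time not attributable to the rule.** After day 168 no WOCBP has a scheduled test. That leaves 181 − 168 = 13 days to 184 − 168 = 16 days, which are not counted here. Check: 28 + 140 + 13 = 181 and 28 + 140 + 16 = 184.

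**Step 5: who could be affected.** Section 5.4.2 puts the first HCV RNA measurement after end of treatment at post-treatment Week 4. A relapse found on schedule therefore cannot lead to other therapy before Week 4. The group is mainly women who stop early for an adverse event or on-treatment breakthrough.

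The documents do not give its size. As assumptions only, let 1% to 10% of 75 subjects stop early and 5% to 25% of subjects be WOCBP:
- low: 75 × 0.01 × 0.05 = 0.0375, about 0.04 women
- high: 75 × 0.10 × 0.25 = 1.875, about 1.9 women

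Both figures come before the further requirement that she start other therapy within 4 weeks, so the true number is smaller.

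**Step 6: after the fix.** With tests kept through Week 24, 6 of 6 are retained and none is lost.

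**The case against.** **The table that might settle it is missing.** The exit sentence and the testing rule both point to Table 5.1-3, the post-treatment schedule, which is not in the supplied text. A footnote there could keep WOCBP on testing. This stands: one can say only that the visible text states no exception. Even with such a footnote, the wording of 3.5 and SAP 2.1 would need to be brought into line with it.

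**Most of the follow-up rules do not conflict.** A reader might infer that the exit rule contradicts Sections 3.1, 3.6 and 5.3.3 and the general sentence in SAP 2.1. The documents do not support that. Those are general rules for subjects who stop study drug, and the exit rule can be read as a carve-out for the subset who then start other therapy. SAP 2.1 states the general rule and then, in the next paragraph, the specific one. The real conflicts are two: the mandatory schedule in 5.3.1 and the consent-only exception sentence in 3.5.

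**The loss is not certain.** Section 5.3.1 is mandatory in tone and specific to WOCBP on ribavirin, while the exit rule says only what a subject should do. A site could reasonably keep testing. This stands, and the figure of 5 of 6 applies only if the exit rule is followed.

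**Other safeguards remain.** The contraception commitment, the counselling duty and the 24-hour pregnancy reporting rule (Sections 3.3.1, 3.5 and 6.4) do not lapse. A reader might infer that these women are left unprotected, which goes too far. But reporting depends on someone learning of the pregnancy, and under Section 5.8.3 the monthly calls are how home-test results are verified. After exit, neither tests nor calls are scheduled.

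**Ending participation is a sponsor's choice.** It is a reasonable one for efficacy data. It does not require ending a safety check that the same protocol makes mandatory.

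**Conclusion.** The point holds in limited form. In the visible text, the exit rule in Section 3.5 and SAP 2.1 has no stated exception for WOCBP, and it conflicts with the testing schedule in 5.3.1 and the consent-only exception sentence in 3.5. If a site follows it, a woman in this position loses 5 of 6 scheduled pregnancy tests over 140 days while her contraception period is still running.

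The per-woman count is firm. It rests on exit at the Week 4 visit and on post-treatment weeks counted from the end of study therapy. The number of women is not known: under the stated assumptions it is at most about 1.9 and may well be zero. The conclusion also depends on Table 5.1-3 containing no exception.

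A reader might extend the loss to women who start other therapy after Week 4. The wording for them combines a prompt exit with completion of the Week 24 procedures, so its effect on testing is unclear and no figure is claimed. Nor does the point touch SVR12, the sample size or the 79% threshold. It is a low-priority safety clarification that is cheap enough to be worth making.

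**What to change.** Check Table 5.1-3 first. Unless it already contains an exception, add one sentence to Protocol Section 3.5: WOCBP who leave the study for other HCV therapy continue the existing monthly home pregnancy tests and telephone contacts through post-treatment Week 24, as consent allows, as safety follow-up only. The same sentence can cover exits after Week 4. Mirror it in SAP Section 2.1 so that the two documents agree; nothing else in the SAP changes.

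The cost is the amendment wording plus up to five home tests and calls per leaver. Weeks 8, 16 and 20 are already telephone-contact weeks under Section 5.8.3. Weeks 12 and 24 would become home tests, which 5.3.1 permits when no office visit is needed. Any positive home test would still go to serum confirmation at the site, as 5.3.1 requires now. Efficacy analyses are unchanged.
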